**Section 6.1. of the CTP:**

*Exact times of measurements outside the permitted time windows will be documented. The acceptable time windows for screening and the end of trial examination are provided in the CTP Flow Chart.*

*Trial measurements and assessments scheduled to occur 'before' trial medication administration at Day 1 are to be performed and completed within a 3 h-period prior to the trial medication administration (including blank values for PK and biomarker). A blank urine sample for PK will be collected within 3 h before drug administration.*

*The acceptable deviation from the scheduled time for vital signs and ECG will be  $\pm 10$  min for the first 4 h after trial medication administration and  $\pm 30$  min thereafter ( $\pm 60$  min for MD part). For laboratory test, the acceptable deviation is  $\pm 30$  min.*

Adherence to time windows will be checked via the consistency check listings at the RPM.

## 7. PLANNED ANALYSIS

The format of the listings and tables will follow the BI guideline "Reporting of clinical trials and project summaries" (6) with the exception of those generated for PK concentrations and parameters following BI standards for PK/PD analysis (10).

PK evaluation will be performed by [REDACTED] and monitored by the department [REDACTED] at [REDACTED]. Descriptive statistics of PK endpoints and plasma concentrations will be presented in Section 15.6 of the CTR.

The individual values of all subjects will be listed. Listings will be sorted by treatment group, subject number and visit (if visit is applicable in the respective listing). AE listings will be sorted by assigned treatment (see [Section 7.8.1](#) below for details). The listings will be contained in Appendix 16.2 (SDL) of the CTR.

The following standard descriptive statistical parameters will be displayed in summary tables of continuous variables:

N	number of non-missing observations
Mean	arithmetic mean
SD	standard deviation
Min	minimum
Median	median
Max	maximum

For plasma concentrations as well as for all PK parameters the following descriptive statistics will additionally be calculated:

CV	arithmetic coefficient of variation
gMean	geometric mean
gCV	geometric coefficient of variation
P10	10 th percentile
Q1	1 st quartile
Q3	3 rd quartile
P90	90 th percentile

The data format for descriptive statistics of plasma concentrations will be identical with the data format of the respective concentrations. The descriptive statistics of PK parameters will be calculated using the individual values with the number of decimal places as provided by the evaluation program. Then the individual values as well as the descriptive statistics will be reported with three significant digits in the CTR.

Tabulations of frequencies for categorical data will include all possible categories and will display the number of observations in a category as well as the percentage (%) relative to the respective treatment group. Percentages will be rounded to one decimal place. The category missing will be displayed if and only if there are actual missing values. Percentages will be

based on all subjects in the respective subject set whether they have non-missing values or not.

#### Exclusion of PK parameters

The ADS “ADPP” (PK parameters) contains column variables APEXC and APEXCO indicating inclusion/exclusion (APEXC) of a PK parameter and an analysis flag comment (APEXCO). All analyses based on the PKS will include parameters if they are not flagged for exclusion, that is APEXC is equal to “Included”.

#### Exclusion of PK concentrations

The ADS “ADPC” (PK concentrations per time-point or per time-interval) contains column variables ACEXC and ACEXCO indicating inclusion/exclusion (ACEXC) of a concentration and an analysis flag comment (ACEXCO). Exclusion of a concentration depends on the analysis flag comment ACEXCO. For example, if ACEXCO is set to ‘ALL CALC’, the value will be excluded for all types of analyses based on concentrations. If ACEXCO is set to ‘DESC STATS’ the value will be excluded from descriptive evaluations per planned time point/time interval. If ACEXCO contains the addition ‘TIME VIOLATION’ or ‘TIME DEVIATION’ the value can be used for further analyses based on actual times. If ACEXCO is set to ‘HALF LIFE’, the value will be excluded from half-life calculation (and, as a consequence, any calculation that relies on  $\lambda_z$ ) only; the value is included for all other analyses.

Further details are given in [\(5\)](#) and [\(11\)](#).

## **7.1 DEMOGRAPHIC AND OTHER BASELINE CHARACTERISTICS**

Only descriptive statistics are planned for this section of the CTR.

## **7.2 CONCOMITANT DISEASES AND MEDICATION**

Only descriptive statistics are planned for this section of the CTR.

Concomitant diseases will be coded according to the most recent version of Medical Dictionary for Drug Regulatory Activities (MedDRA). Medications will be coded using the World Health Organization Drug Dictionary (WHO-DD). The coding version number will be displayed as a footnote in the respective output. Concomitant non-drug therapies will be coded according to the most recent version of MedDRA.

A medication will be considered concomitant to a dose group if it

- is ongoing at the time of study drug administration, or
- starts within the analysis phase of the respective treatment (see [Section 6.1](#) for a definition of treatments and analysis phases).

The relevance of the concomitant therapies to the evaluation of PK will be decided no later than at the RPM.

## **7.3 TREATMENT COMPLIANCE**

### **Section 4.3 of the CTP:**

*Compliance will be assured by administration of all trial medication in the trial site under supervision of the investigating physician or a designee. The measured plasma concentrations and/or urinary excretion of trial medication will provide additional confirmation of compliance.*

*Subjects who are non-compliant (for instance, who do not appear for scheduled visits or violate trial restrictions) may be removed from the trial and the CRF will be completed accordingly (for further procedures, please see CTP Section 3.3.4.1).*

Treatment compliance will not be analysed as a specific endpoint. Any deviations from complete intake will be addressed in the RPM (cf. [Section 6.2](#)) and described in the CTR.

## **7.4 PRIMARY ENDPOINTS**

### **7.4.1 Primary analysis of the primary endpoints**

For the SRD and MD parts of this trial, the primary endpoint for assessment of safety and tolerability of BI 1323495 is the percentage of subjects with drug-related AEs. The analysis will be based on the treated set (TS) and will be descriptive in nature. Refer to [Section 7.8.1](#) for a description of the analysis of AEs, and in particular the analysis of the percentage of subjects with treatment-emergent drug-related AEs.

For the DDI part of this trial, relative bioavailability of BI 1323495 in plasma is to be determined based on the primary PK endpoints  $AUC_{0-\infty}$  and  $C_{max}$  on the PKS (cf. [Section 5.1](#)).

### **Section 7.3.1 of the CTP:**

*The statistical model used for the analysis of the primary endpoints will be an analysis of variance (ANOVA) model on the logarithmic scale. That is, the PK endpoints will be log-transformed (natural logarithm) prior to fitting the ANOVA model. This model will include effects accounting for the following sources of variation: subject and treatment. The effect 'subject' will be considered as random, whereas the effect 'treatment' will be considered as fixed. The model is described by the following equation:*

$$y_{km} = \mu + s_m + \tau_k + e_{km}, \text{ where}$$

*$y_{km}$  = logarithm of response measured on subject  $m$  receiving treatment  $k$ ,*

*$\mu$  = the overall mean,*

*$s_m$  = the effect associated with the  $m^{th}$  subject,  $m = 1, 2, \dots, n$ ,*

*$\tau_k$  = the  $k^{th}$  treatment effect,  $k = 1, 2$ ,*

$e_{km}$  = the random error associated with the  $m^{th}$  subject who received treatment  $k$ , where  $s_m \sim N(0, \sigma_B^2)$  i.i.d.,  $e_{km} \sim N(0, \sigma_W^2)$  i.i.d. and  $s_m, e_{km}$  are independent random variables. The indices 'B' and 'W' correspond to 'between' and 'within' variability, respectively.

Point estimates for the ratios of the geometric means (test/reference) for the primary endpoints (see CTP Section 2.1.2) and their two-sided 90% confidence intervals (CIs) will be provided.

For each endpoint, the difference between the expected means for  $\log(T)$ - $\log(R)$  will be estimated by the difference in the corresponding adjusted means (Least Squares Means). Additionally, their two-sided 90% confidence intervals will be calculated based on the residual error from the ANOVA and quantiles from the  $t$  distribution. These quantities will then be back transformed to the original scale to provide the point estimate and 90% CIs for each endpoint.

The implementation for this analysis will be accomplished by using the CSD macros based on PKS. The following SAS code can be used:

```
PROC MIXED DATA=indata;
  CLASS subject treatment;
  MODEL logpk = treatment / DDFM=KR;
  RANDOM subject;
  LSMEANS treatment / PDIFF CL ALPHA=0.1;
  ESTIMATE 'T-R' treatment -1 1;
RUN;
```

#### **7.4.2 Sensitivity analysis, subgroup analysis, exploratory analysis of the primary endpoints**

##### **Section 7.3.1 of the CTP:**

*The same statistical model as stated above will be repeated for the primary endpoints but with 'subjects' considered as fixed effect.*

The following SAS code can be used to fit the model:

```
PROC GLM DATA=indata;
  CLASS subject treatment;
  MODEL logpk = treatment subject;
  LSMEANS treatment / PDIFF CL ALPHA=0.1;
  ESTIMATE 'T-R' treatment -1 1;
RUN;
```

##### **Section 7.3.1 of the CTP:**

*In addition to the model-based approach, all parameters will be calculated and analysed descriptively. Furthermore, mean plasma concentration time curves as well as individual profiles will be provided.*

## **7.5 SECONDARY ENDPOINTS**

### **7.5.1 Key secondary endpoints**

This section is not applicable as no key secondary endpoint has been specified in the protocol.

### **7.5.2 Secondary endpoints**

Secondary PK endpoints in all trial parts will be assessed descriptively. The secondary endpoint in the DDI part will be assessed statistically using the same methods as described for the primary PK endpoints (cf. [Section 7.4.1](#))

#### **Section 7.3.2. of the CTP:**

*SRD part (both EM and PM):*

*Dose proportionality will be explored via graphical checks and if applicable via the power model stated below. The analysis will be performed for the pharmacokinetic endpoints  $AUC_{0-\infty}$  and  $C_{max}$  specified in CTP Section 2.1.3.*

*The power model describes the functional relationship between the dose level and PK endpoint on the log scale via*

$$y_{km} = \log(x_{km}) = \mu + b \cdot \log(D_k) + e_{km},$$

*where*

[figure not shown]
$y_{km}$  logarithm of response (PK parameter) measured on subject  $m$  receiving dose  $k$ ,  
 $\mu$  the overall mean,  
 $\beta$  slope parameter of linear regression line,  
 $D_k$  level of dose  $k$ ,  $k=1, \dots, 3$ ,  
 $e_{km}$  the random error associated with the  $m^{th}$  subject who was administered dose level  $k$  where  $(e_{km} \sim N(0, \sigma^2))$  iid.

[figure not shown]
*The slope parameter  $\beta$  together with its two-sided 90% confidence interval will be estimated. Additionally, the r-fold change  $r^{\beta-1}$  together with its 90% CI will be derived.*

*DDI part (only PM):*

*The secondary endpoints  $AUC_{0-tz}$  (refer to CTP Section 2.1.3) will be assessed statistically using the same methods as described for the primary PK endpoints in Section CTP 7.3.1.*

In SRD part, the dose proportionality will be assessed and reported for EM and PM subjects separately.

## **7.7 EXTENT OF EXPOSURE**

Descriptive statistics are planned for this section of the report based on the TS.

## **7.8 SAFETY ANALYSIS**

All safety analyses will be performed on the TS.

### **7.8.1 Adverse Events**

AEs will be coded with the most recent version of MedDRA.

The analyses of AEs will be descriptive in nature. All analyses of AEs will be based on the number of subjects with AEs and not on the number of AEs.

For further details on summarization of AE data, please refer to "Analysis and Presentation of Adverse Event Data from Clinical Trials" ([7](#)) and "Handling of missing and incomplete AE dates" ([3](#)).

The analysis of AEs will be based on the concept of treatment emergent AEs. That means that all AEs will be assigned to screening, on-treatment or follow-up phases as defined in [Section 6.1](#). AEs will be analysed based on actual treatments, as defined in [Table 6.1: 1](#) and [Table 6.1:2](#).

An overall summary of AEs will be presented. This overall summary will comprise summary statistics for the class of adverse events of special interest (AESIs).

#### **Section 5.2.6.1.4 of the CTP:**

*The following are considered as AESIs:*

##### *Hepatic injury*

*A hepatic injury is defined by the following alterations of hepatic laboratory parameters:*

- *an elevation of AST (aspartate transaminase) and/or ALT (alanine transaminase)  $\geq 3$  folds ULN combined with an elevation of total bilirubin  $\geq 2$  folds ULN measured in the same blood draw sample, or*
- *Aminotransferase (ALT, and/or AST) elevations  $\geq 10$  folds ULN.*

According to ICH E3 ([8](#)), in addition to Deaths and Serious Adverse Events, 'other significant' AEs need to be listed in the clinical trial report. These will be any non-serious adverse event that led to an action taken with study drug (e.g. discontinuation or dose reduced or interrupted).

The frequency of subjects with AEs will be summarised by treatment, primary System Organ Class (SOC) and preferred term. AEs which were considered by the investigator to be drug related will be summarised. Separate tables will also be provided for subjects with SAEs and subjects with AESIs. AEs will also be summarised by maximum intensity.

The SOCs and preferred terms within SOCs will be sorted by descending frequency over all treatment groups.

For disclosure of AE data on ClinicalTrials.gov, the frequency of subjects with non-serious AEs occurring with an incidence of greater than 5 % (in preferred terms) will be summarised

by treatment, primary SOC and preferred term. The frequency of subjects with SAEs will also be summarised.

For disclosure of AE data in the EudraCT register, the frequency of AEs, the frequency of non-serious AEs with an incidence of greater than 5 % (in preferred terms) and the frequency of SAEs will be summarised.

For support of lay summaries, the frequency of subjects with drug-related SAEs will be summarised by treatment, primary SOC and preferred term.

## **7.8.2      Laboratory data**

The analyses of laboratory data will be descriptive in nature and will be based on BI standards "Display and Analysis of Laboratory Data" ([9](#)).

Analyses will be based on normalised values, which means transforming to a standard unit and a standard reference range. The original values will be analysed if the transformation into standard unit is not possible for a parameter.

Descriptive statistics of laboratory values over time and for the difference from baseline (see [Section 6.7](#)) will be provided. Frequency tables of changes between baseline and last value on treatment with respect to the reference range will be presented.

Unscheduled measurements of laboratory data will be assumed to be repeat measurements of the most recent scheduled measurement (e.g. for follow-up or confirmation of a particular value). Therefore, unscheduled measurements will be assigned to the planned time point of the previous scheduled measurement. Descriptive statistics will be calculated by planned time point based on the worst value of the subject at that planned time point (or assigned to that planned time point).

Possibly clinically significant abnormal laboratory values are only those identified either in the Investigator's comments or at the Report Planning Meeting at the latest. It is the Investigator's responsibility to decide whether a lab value is clinically significant abnormal or not. Standard or project-specific rules for flagging clinically significant values in an automated manner will not be applied in this study.

Clinically relevant findings in laboratory data will be reported as baseline conditions (prior to first administration of study treatment) or as AEs (after first administration of study treatment) if judged clinically relevant by the investigator, and will be analysed as such.

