## FLOW CHART

SRD part

				Event and comment	Safety laboratory 	PK blood 	PK urine 	Medical Examination	Vital signs (BP, PR) 	12-lead ECG 	Questioning for AEs and concomitant therapy 
	Visit	Day	Planned time (relative to BI 1323495 or placebo administration [h:min])	Approximate clock time of actual day [h:min]							
SCR	1	-28 to -8		Screening (SCR)  including pharmacogenomics test UGT2B17	x A,7			x	x	x	
Treatment period	2	-1	-18:00	15:00	Ambulatory visit 	x B,7					x
			-12:00	21:00	Admission to trial site						
		1 	-2:00	07:00	Allocation to treatment		x	x	x	x 	x
			-0:30	08:30	Standardized breakfast						
			0:00	09:00	BI 1323495 or placebo administration		▲				
			0:20	09:20		x			x	x	x
			0:40	09:40		x			x	x	x
			1:00	10:00		x			x	x	x
			1:30	10:30		x			x	x	x
			2:00	11:00	240 mL fluid intake	x			x	x	x
			3:00	12:00		x			x	x	x
			4:00	13:00	240 mL fluid intake, thereafter lunch 	x B	x	+	x	x	x
			5:00	14:00		x				x	
			6:00	15:00		x			x	x	x
			7:00	16:00		x				x	
2	2	14	8:00	17:00	Snack(voluntary) 	x	+		x	x	x
			9:00	18:00		x				x	
			10:00	19:00	Dinner 	x			x	x	x
			12:00	21:00		x	+		x	x	x
		2	24:00	09:00	Breakfast 	x B	x	+	x	x	x
			28:00	13:00	Lunch 						
			32:00	17:00	Snack(voluntary)						
			34:00	19:00	Dinner 	x	+			x	x
EOT	3	48:00	09:00	Discharge from trial site	x	▼			x	x	
		72:00	09:00	Ambulatory visit	x				x	x	
		96:00	09:00	Ambulatory visit	x				x	x	
		120:00	09:00	Ambulatory visit	x 					x	
		144:00	09:00	Ambulatory visit	x 					x	
		168:00	09:00	Ambulatory visit	x B	x 		x	x	x	x
		9 to 15		End of trial (EOT) examination 	x A			x	x	x	x

PK: pharmacokinetics, ECG: electrocardiogram, BP: blood pressure, PR: pulse rate, AE: adverse event

Clock time should be adjusted based on actual administration time

Proprietary confidential information © 2021 Boehringer Ingelheim International GmbH or one or more of its affiliated companies

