### Clinical experience

At the time of preparing this trial protocol, three Phase I trials with administration of single doses of BI 1323495 to healthy male volunteers have been completed, trials 1405-0001 was first-in-man trial, 1405-0007 investigated relative BA (Bioavailability) and food effect, and 1405-0009 investigated drug interaction with itraconazole. In addition to this, 1405-0002, multiple rising dose (MRD) trial in healthy subjects is currently ongoing, and analysis of the DDI trial (1405-0015) with Rosuvastatin (BRCP and OATP1B1 substrate) and Dabigatran (P-gp substrate) is ongoing.

In the single rising dose (SRD) trial 1405-0001, single-dose treatment with up to 600 mg BI 1323495 or placebo was safe and well tolerated. There was no relationship between the occurrence of AEs and dose. Three AEs in subjects receiving BI 1323495 were judged as moderate in intensity, all other AEs were classified as mild. No severe or serious AEs were reported. The most frequently reported treatment-emergent AE was headache, reported for 6 out of 48 subjects (12.5%) receiving BI 1323495 and 2 out of 15 subjects (13.3%) receiving placebo. The next-most frequently reported treatment-emergent AEs were fatigue and diarrhea, each reported for 2 out of 48 subjects (4.2%) receiving BI 1323495. In one subject receiving 300 mg BI 1323495, a mild (<2-fold upper limit of normal [ULN]) and transient elevation of alanine transaminase (ALT) and glutamate dehydrogenase (GLDH) was reported.

The level of exposure to BI 1323495 was dependent on the expression pattern of the enzyme UGT2B17 in the intestine. While homozygous and heterozygous carriers of the wild type allele (UGT2B17 \*1/\*1 and \*1/\*2) could not be distinguished based on their exposures, AUCs and  $C_{max}$  were increased in subjects with homozygous deletion of UGT2B17 (\*2/\*2), compared with the other genotypes (Table [1.2.1: 1](#)) [[c26492551](#)].

After the first-pass metabolism, the same pharmacokinetic properties apply to all genotypes. gMean (geometric mean) plasma exposure increased in a less than dose-proportional manner. Multiple plasma concentration peaks were observed in the profiles of nearly all subjects treated. Subjects with genotype \*2/\*2 did not show as many peaks as the other genotypes in the concentration-time profiles. The terminal half-life was similar over all dose groups, except for being longer in the 600 mg dose group.

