### 1.2.3. Residual Effect Period

The Residual Effect Period (REP, i.e., the period after the last dose with measurable drug levels and/or pharmacodynamic effects still likely to be present) of BI 1323495 is approximately 7 days.

When given together with itraconazole (Treatment T), it is expected that plasma exposure of BI 1323495 could be increased (albeit within the exposures explored in the clinical trial

Proprietary confidential information © 2021 Boehringer Ingelheim International GmbH or one or more of its affiliated companies

1405-0001), and the time of relevant plasma exposure could be prolonged. This might result in a prolonged period in which adverse effects could potentially occur.

For the use of itraconazole in Treatment T, the REP is defined as 9 days after last administration of itraconazole on Day 7 in Period 2.

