#### **5.2.3. Safety laboratory parameters**

For the assessment of laboratory parameters, blood and urine samples will be collected by the trial site at the time points indicated in the [Flow Chart](#) after the subjects have fasted for at least 10 h, except 4 h post dosing on Day 1 of SRD part and screening. For retests, at the discretion of the investigator or designee, overnight fasting is not required. The parameters that will be determined are listed in Tables [5.2.3: 1](#) and [5.2.3: 2](#). Reference ranges will be provided in the ISF, Section [10](#).

Manual differential white blood cell count or urine sediment examinations will only be performed if there is an abnormality in the automatic blood cell count or in the urinalysis, respectively.

Table 5.2.3: 1 Routine laboratory tests

Functional lab group	BI test name [comment/abbreviation]	A 	B 	C 	D 
Haematology	Haematocrit	X	X	--	X
	Haemoglobin	X	X	--	X
	Red Blood Cell Count/Erythrocytes	X	X	--	X
	White Blood Cells/Leucocytes	X	X	--	X
	Platelet Count/Thrombocytes (quant)	X	X	--	X
Automatic WBC relative	Neutrophils/Leukocytes; Eosinophils/Leukocytes; Basophils/ Leukocytes; Monocytes/Leukocytes; Lymphocytes/Leukocytes	X	X	--	X
Automatic WBC differential	Neutrophil, absol.; Eosinophils, absol.; Basophils, absol.; Monocytes, absol.; Lymphocytes, absol.	X	X	--	X
Manual differential WBC (if automatic differential WBC is abnormal and clinically relevant in the opinion of the investigator)	Neut. Poly (segs; Neutrophils Bands; Eosinophils/Leukocytes; Basophils/ Leukocytes; Monocytes/ Leukocytes; Lymphocytes/Leukocytes;				
Coagulation	Activated Partial Thromboplastin Time	X	--	--	--
	Prothrombin time	X	--	--	--
	INR (International Normalization Ratio)	X	--	--	--
	Fibrinogen	X	X	--	--
Enzymes	AST [Aspartate transaminase] /GOT	X	X	X	--
	ALT [Alanine transaminase] /GPT	X	X	X	--
	Alkaline Phosphatase	X	X	X	--
	Gamma-Glutamyl Transferase	X	X	X	--
	Creatine Kinase [CK]	X	X	--	--
	Creatine Kinase Isoenzyme MB [only if CK is elevated and clinically relevant in the opinion of the investigator]	X	X	--	--
Hormones	Thyroid Stimulating Hormone	X	--	--	--
Substrates	Glucose (Plasma)	X	X	--	--
	Creatinine	X	X	--	--
	GFR/ CKD-EPI	X	X	--	--
	Bilirubin, Total	X	X	--	--
	Bilirubin, Direct	X	X	--	--
	Protein, Total	X	X	--	--
	C-Reactive Protein (Quant)	X	X	--	--
	Cholesterol, total	X	--	--	--
Electrolytes	Triglyceride	X	--	--	--
	Sodium	X	X	--	--
	Potassium	X	X	--	--

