#### **7.3.4. Safety analyses**

Safety will be assessed as defined by the endpoints listed in Section [2.1.2](#) and [2.2.2.1](#) based on the treated set (TS). Safety analyses will be descriptive in nature and will be based on BI standards.

For all analyses the treatment actually administered (= treatment at onset) to the subject will be used (any deviations from the randomised treatment will be discussed in the minutes of the Report Planning Meeting).

Treatments will be compared in a descriptive way. In SRD part, the placebo group in the safety evaluation will consist of all subjects treated with placebo, regardless of the dose group in which they were treated. The test treatment groups will be compared to the placebo group in a descriptive way. In DDI part, the test treatment groups (BI 1323495+itraconazole) will be compared to the reference group (BI 1323495 alone) in a descriptive way. Tabulations of frequencies/proportions will be used for the evaluation of categorical (qualitative) data, and tabulations of descriptive statistics will be used to analyse continuous (quantitative) data.

Measurements (such as ECGs, vital signs, or laboratory parameters) or AEs will be assigned to treatments (see Section [4.1](#)) based on the actual treatment at the planned time of the measurement or on the recorded time of AE onset (concept of treatment-emergent AEs). Therefore, measurements planned or AEs recorded prior to intake of trial medication will be assigned to the screening period, those between the first trial medication intake and end of REP (see Section [1.2.3](#)) will be assigned to the treatment period. Events occurring after the REP but prior to next intake or end of trial termination date will be assigned to 'follow-up'. These assignments including the corresponding time intervals will be defined in detail in the TSAP. Note that AEs occurring after the last per protocol contact but entered before database lock will be reported to Pharmacovigilance only and will not be captured in the trial database.

Additionally, further treatment intervals (called analysing treatments) may be defined in the TSAP in order to provide summary statistics for other than above periods, such as combined treatments, on-treatment totals, or periods without treatment effects (such as screening and post-trial intervals).

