## **6. GENERAL ANALYSIS DEFINITIONS**

### **6.1 TREATMENTS**

For basic study information on treatments to be administered, assignment of treatment groups, and selection of doses, cf. Section 4 of the CTP.

**SRD part, PM:** 24 subjects were planned to be treated with

- doses of 10 mg (1 x 10 mg tablet), 30 mg (3 x 10 mg tablets), or 100 mg (2 x 50 mg tablets) of BI 1323495 on Day 1 (test treatment)
- or matching placebo (reference treatment).

**SRD part, EM:** 12 subjects were planned to be treated with

- doses of 30 mg (3 x 10 mg tablets), 70 mg (2 x 10 mg tablets and 1 x 50 mg tablet) or 150 mg (3 x 50 mg tablets) of BI 1323495 on Day 1 (test treatments)
- or matching placebo (reference treatment).

**MD part, PM:** 24 subjects were planned to be treated with

- doses of 30 mg (3 x 10 mg tablets twice daily for 10 days and single dose on Day 11) or 60 mg (1 x 10 mg tablet and 1 x 50 mg tablet once daily for 11 days) of BI 1323495 (test treatment)
- or matching placebo (reference treatment).

**DDI part, PM:** Subjects were planned to be treated with

- a dose of 10 mg (1 tablet as single dose on Day 1 of period 1) of BI 1323495 (reference treatment)
- and – after a washout period of at least 11 days – doses of 10 mg (1 tablet as single dose on Day 1) of BI 1323495 and 200 mg of itraconazole once daily on Days -3 to 7 (test treatment).

In the SRD and MD parts, subjects are planned to be randomised within each dose group in a 3:1 ratio (test treatment to placebo). In the DDI part, randomisation is not applicable, because all subjects are planned to receive the same treatment in the same order.

The following study phases will be defined for the analysis of AEs:

Table 6.1: 1 Analysis phases and labels for statistical analyses in the SRD and MD parts

Study analysis phase	Label	Start	End
Screening 	Screening	Date of informed consent	Date/time of first administration of BI 1323495 or placebo
On treatment	Placebo SRD PM 10 mg, SRD PM 30 mg, SRD PM 100 mg, SRD EM 30 mg, SRD EM 70 mg, SRD EM 150 mg, MD PM 30 mg BID, MD PM 60 mg QD, respectively	Date/time of first administration of BI 1323495 or placebo	Date/time of last administration of BI 1323495 or placebo + REP (7 days, i.e., 7 * 24 h)  or  12:00 a.m. on day after last contact date  (whichever occurs first)

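### Laboratory shift tables run from baseline to the last on-treatment value (168 h after a single dose in the SRD part), so an earlier excursion that has resolved is counted as no shift

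*SAP*

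**What the plan says.** SAP 7.8.2 plans descriptive statistics of laboratory values over time and for the difference from baseline. It then adds the reference-range display: "Frequency tables of changes between baseline and last value on treatment with respect to the reference range will be presented". The same section uses a subject's worst value when several results belong to one planned time point. That rule is written for the by-time-point statistics, not for the shift table. Automated flagging of clinically significant values is switched off.

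What counts as on treatment comes from two places:

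- SAP Table 6.1: 1 ends the phase for the SRD and MD parts at "Date/time of last administration of BI 1323495 or placebo + REP (7 days, i.e., 7 * 24 h"), or at last contact if that is earlier. The table is introduced for AEs.
- Protocol 7.3.4 extends the same logic to measurements. They are assigned "based on the actual treatment at the planned time of the measurement", and "those between the first trial medication intake and end of REP" belong to the treatment period.

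Protocol 1.2.3 gives the source of the interval: the residual effect period (REP) of "BI 1323495 is approximately 7 days".

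The SRD flow chart places post-dose safety laboratory samples at 4 h, 24 h and 168 h ("168:00 09:00 Ambulatory visit x B"), followed by the end-of-trial examination on Day 9 to 15.

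**The concern.** A last-value shift table answers whether a subject was out of range at the end of the phase. For a single dose, the more useful question is whether the subject went out of range at any time after dosing. With a sample exactly at the end of the REP, the planned table describes recovery rather than effect.

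This matters because Protocol 1.4.2 names liver, kidney and coagulation findings from preclinical work and relies on safety laboratory monitoring to watch for them. The other routes do not give the same count:

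- Summary statistics by time point do not count subjects who crossed the range.
- Listings do not tabulate by treatment.
- AE tables depend on the investigator judging the value clinically relevant, and Protocol 4.1.5.1 says that the investigator knows the treatment.

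The shift table is the one by-treatment count named in the SAP that does not rest on that judgement.

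**Working it through.** **Step 1. End of the phase.** REP = 7 x 24 h = 168 h, which reproduces the figure in SAP Table 6.1: 1. For DDI treatment T, SAP Table 6.1: 2 ends the phase 9 days after the last itraconazole dose. That dose is at 143 h, so the phase ends at 143 + 9 x 24 = 359 h after the BI 1323495 dose.

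**Step 2. Last scheduled on-treatment sample**, from the flow charts and Protocol Table 5.2.3: 1. Set D is haematology only, so chemistry in the MD part comes from set B. SRD and DDI hours count from the BI 1323495 dose; MD hours count from the final dose at 240:00.

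| Part | Laboratory times (h) | Phase end (h) | Last on-treatment value |
|---|---|---|---|
| SRD | 4, 24, 168 | 168 | 168 h |
| MD chemistry | 0 (pre-dose), 48 | 168 | 288 - 240 = 48 h |
| MD haematology | 2, 12, 24, 48, 72, 120, 168 | 168 | 408 - 240 = 168 h |
| DDI treatment R | 24, 71 | 168 | 71 h |
| DDI treatment T | 23, 71, 119, 167 | 359 | 167 h |

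**Step 3. The boundary.** The SRD 168:00 sample, and the MD haematology sample at 408:00, lie exactly where Table 6.1: 1 ends the on-treatment phase and starts follow-up. Protocol 7.3.4 assigns by planned time and sends to follow-up only what occurs after the REP. A planned 168 h sample is not after it, so the protocol wording puts it on treatment. The SAP does not state this. If the end point were excluded, the last values would be 24 h (SRD) and 120 h (MD haematology).

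**Step 4. The rule applied to example SRD subjects** with a normal baseline. Values are multiples of the upper limit of normal (ULN) and are invented for illustration.

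| 4 h, 24 h, 168 h | Last = 168 h | Last = 24 h | Worst value |
|---|---|---|---|
| 1.5, 0.8, 0.7 | no shift | no shift | high |
| 1.1, 1.8, 0.9 | no shift | high | high |
| 0.8, 2.5, 0.95 | no shift | high | high |
| 0.8, 1.8, 1.2 | high | high | high |

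**Step 5. How large an excursion could be missed by the table.** Assumptions not in the documents: baseline 0.5 x ULN, and an excess over baseline that halves every h hours from 24 h on. The value is back in range at 168 h if the 24 h peak is at most 0.5 + 0.5 x 2^(144/h), because 168 - 24 = 144. For h = 24, 48, 72 and 96 this gives 32.5, 4.5, 2.5 and 1.9 x ULN. The range is wide and only shows that the answer depends on recovery speed.

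**The case against.** The strongest reply is that this is a display preference in a purely descriptive analysis, and that early values are already reported. Much of that stands:

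- The by-time-point statistics include minimum and maximum (SAP Section 7), so a 4 h or 24 h excursion appears as the group maximum or minimum.
- Protocol 7.3.4 highlights out-of-range values in the listings, and SRD dose groups have only 6 or 3 active subjects.
- Findings judged clinically relevant enter the AE tables, and hepatic injury has its own AESI table.
- The dose-escalation review in Protocol 3.1 does not use the shift table.

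A reader might infer more than the documents support:

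- *That transient abnormalities go unreported.* They do not, for the reasons above. What is switched off is automated flagging of clinically significant values, not reference-range highlighting.
- *That the 4 h and 24 h samples can never affect the table.* Two of the three SRD times drop out only when the 168 h sample is present and counted as on treatment. If it is missing, the 24 h value is used.
- *That 24 h is near peak exposure.* Median fed tmax in the food-effect trial was 2.00 h (Protocol 1.2.1), and SRD dosing is fed.
- *That an event already seen would be lost.* Protocol 1.2.1 says that in one subject a mild "transient elevation of alanine transaminase (ALT) and glutamate dehydrogenase (GLDH) was reported". No time course is given, and GLDH is not in this trial's laboratory panel, so the example proves nothing about this table.
- *That no other reference-range table will be produced.* SAP 7.8.2 relies on a sponsor laboratory-display standard that is not available here and may add some.

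A worst-value table also has a real drawback. Laboratory samples are fasted "except 4 h post dosing on Day 1 of SRD part and screening". The 4 h SRD sample follows breakfast, so parameters such as glucose could show meal-related shifts.

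**Conclusion.** The point holds as a limited one. As planned, an SRD value out of range at 4 h or 24 h and back in range at 168 h is tabulated as no shift. The same mechanism acts at 48 h (MD chemistry), 168 h (MD haematology) and 71 h (DDI treatment R). If the 168 h sample were left out of the phase, it would still affect a 4 h abnormality that is gone by 24 h.

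What changes is a set of counts in one family of safety tables. The primary endpoint, the pharmacokinetic estimates and the escalation decisions do not change. The number of subjects affected cannot be estimated from the documents.

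The conclusion assumes that laboratory data follow the phase rule of Protocol 7.3.4 by planned time, and that the sponsor standard adds no worst-value shift table. It is worth acting on because the remedy is cheap and fits the worst-value rule already in the same SAP section.

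**What to change.** In SAP 7.8.2:

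1. Add shift tables from baseline to the highest and, separately, to the lowest on-treatment value relative to the reference range, by treatment and beside placebo. Keep the last-value table.
2. Footnote or separate parameters affected by the non-fasted 4 h SRD sample, for example glucose.
3. State that laboratory samples are assigned by planned time and that the planned 168 h sample belongs to the on-treatment phase. The same sentence settles the MD haematology sample at 408:00.

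The cost is one extra set of standard tables and two or three sentences. The downside is that extreme values cross the range more often by chance, and the placebo comparison is small: 3 x 2 = 6 PM and 3 x 1 = 3 EM subjects in the SRD part. The new tables should be read against placebo and not alone.
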